4.6.2. Benefit Assessment

Subjects will receive single or combination of long-acting bronchodilator therapies approved for maintenance treatment of COPD. Participating subjects in this study will contribute to the process of further characterizing the benefit of these long-acting bronchodilators with respect to PROs and symptoms in the treatment of COPD.

Specific benefits associated with the study design and procedures include the following:

- Subjects will receive treatments approved for the treatment of COPD that have been shown to be effective in the population under study
- All subjects will receive albuterol/salbutamol for use “as needed” for relief of COPD symptoms
- The combination of study procedures of spirometry, CAT, SGRQ, TDI, E-RS will provide the study subjects with a comprehensive evaluation of their symptoms, health status and COPD disease severity. Subjects will also be monitored throughout the study for any worsening of COPD symptoms or decline in general health. Finally smoking cessation counselling will also be provided.

4.6.3. Overall Benefit: Risk Conclusion

Taking into account the measures taken to minimize risk to subjects participating in this study, the potential risks identified in association with UMEC/VI, UMEC, salmeterol and with study procedures are justified by the anticipated benefits from active treatments that may be afforded to patients with COPD.

5. SELECTION OF STUDY POPULATION AND WITHDRAWAL CRITERIA

Specific information regarding warnings, precautions, contraindications, adverse events, and other pertinent information on the GSK investigational product or other study treatment that may impact subject eligibility is provided in the IBs, [GlaxoSmithKline Document Number [RM2006/00835/09](#)], [GlaxoSmithKline Document Number [RM2009/00437/07](#)] and product labels.

Deviations from inclusion and exclusion criteria are not allowed because they can potentially jeopardize the scientific integrity of the study, regulatory acceptability or subject safety. Therefore, adherence to the criteria as specified in the protocol is essential.

5.1. Inclusion Criteria

French subjects: In France, a subject will be eligible for inclusion in this study only if either affiliated to or a beneficiary of a social security category.

A subject will be eligible for inclusion in this study only if all of the following criteria apply:

AGE
1. 40 years or older at date of signing informed consent

TYPE OF SUBJECT AND DIAGNOSIS INCLUDING DISEASE SEVERITY
2. Outpatient with a diagnosis of COPD in accordance with the definition of the American Thoracic Society/European Respiratory Society (ATS/ERS) [Celli , 2004].
3. FEV₁ : Persistent airflow limitations as indicated by: A pre and post-albuterol/salbutamol FEV ₁ /FVC ratio of <0.70 and a post-albuterol/salbutamol FEV ₁ of $\geq 30\%$ to $\leq 80\%$ predicted normal values at Screening Visit 1. Predicted values will be based upon the ERS Global Lung Function Initiative [Quanjer , 2012].
4. CAT score : A CAT score of ≥ 10 at Screening Visit 1

Smoking History
5. Current or former cigarette smokers with a history of cigarette smoking of ≥ 10 pack-years [number of pack years = (number of cigarettes per day / 20) x number of years smoked (e.g. 20 cigarettes per day for 10 years, or 10 cigarettes per day for 20 years both equal 10 pack-years)]. Former smokers are defined as those who have stopped smoking for at least 6 months prior to Visit 1. Pipe and/or cigar use cannot be used to calculate pack-year history.

SEX
6. Male and female subjects are eligible to participate in the study A female subject is eligible to participate if she is not pregnant (as confirmed by a negative urine human chorionic gonadotrophin (hCG) test), not lactating, and at least one of the following conditions applies: a. Non-reproductive potential defined as: Pre-menopausal females with one of the following: 
• Documented tubal ligation• Documented hysteroscopic tubal occlusion procedure with follow-up confirmation of bilateral tubal occlusion• Hysterectomy• Documented Bilateral Oophorectomy Postmenopausal defined as 12 months of spontaneous amenorrhea. In questionable cases a blood sample with simultaneous follicle stimulating hormone (FSH) and estradiol levels consistent with menopause must be tested. Females on hormone replacement therapy (HRT) and whose menopausal status is in doubt will be required to use one of the highly effective contraception methods if they wish to continue their HRT during the study.

Otherwise, they must discontinue HRT to allow confirmation of post-menopausal status prior to study enrolment.

b. Reproductive potential and agrees to follow one of the options listed in the Modified List of Highly Effective Methods for Avoiding Pregnancy in Females of Reproductive Potential (FRP) ([Appendix 7](#)) from 30 days prior to the first dose of study medication and until [at least five terminal half-lives OR until any continuing pharmacologic effect has ended, whichever is longer] after the last dose of study medication and completion of the follow-up visit.

The investigator is responsible for ensuring that subjects understand how to properly use these methods of contraception.

INFORMED CONSENT

7. **Capable of giving signed informed consent** prior to study participation, which includes compliance with the requirements and restrictions listed in the consent form and in this protocol.

5.2. Exclusion Criteria

A subject will not be eligible for inclusion in this study if any of the following criteria apply:

CONCURRENT CONDITIONS/MEDICAL HISTORY (INCLUDES LIVER FUNCTION)

1. **Asthma:** A current diagnosis of asthma. (Subjects with a prior history of asthma are eligible if they have a current diagnosis of COPD, which is the primary cause of their respiratory symptoms).
2. **Alpha-antitrypsin deficiency:** Subjects with known α 1-antitrypsin deficiency as the underlying cause of COPD
3. **Other respiratory disorders:** Subjects with active tuberculosis are excluded. Subjects with other respiratory disorders (e.g. clinically significant: bronchiectasis, sarcoidosis, lung fibrosis, pulmonary hypertension, interstitial lung diseases) are excluded if these conditions are the primary cause of their respiratory symptoms.
4. **Unstable liver disease:** Current active liver or biliary disease (with the exception of Gilbert's syndrome or asymptomatic gallstones or otherwise stable chronic liver disease per investigator assessment).
 - Stable chronic liver disease should generally be defined by the absence of ascites, encephalopathy, coagulopathy, hypoalbuminaemia, oesophageal or gastric varices, or persistent jaundice, or cirrhosis.
 - Chronic stable hepatitis B and C (e.g., presence of hepatitis B surface antigen (HBsAg) or positive hepatitis C antibody test result or within 3 months prior to first dose of study treatment) are acceptable if subject otherwise meets entry

criteria

5. **Unstable or life threatening cardiac disease:** Investigational Product should be used with caution in subjects with severe cardiovascular disease. In the opinion of the investigator, use should only be considered if the benefit is likely to outweigh the risk in conditions such as:
 - Myocardial infarction or unstable angina in the last 6 months
 - Unstable or life threatening cardiac arrhythmia requiring intervention in the last 3 months
 - NYHA Class IV heart failure
6. **12 Lead ECG:** The Investigator will determine the clinical significance of each abnormal ECG finding in relation to the subject's medical history and exclude subjects who would be at undue risk by participating in the trial. Subjects with the following abnormalities are excluded from participation in the study:
 - Atrial fibrillation with rapid ventricular rate >120 bpm
 - Sustained or non-sustained ventricular tachycardia
 - Second degree heart block Mobitz type II or third degree heart block (unless pacemaker or defibrillator had been inserted)
7. **Antimuscarinic effects:** Subjects with medical conditions such as narrow-angle glaucoma, urinary retention, prostatic hypertrophy, or bladder neck obstruction should be excluded unless, in the opinion of the study physician, the benefit outweighs the risk.
8. **Other disease abnormalities:** Any subject who is considered unlikely to survive the duration of the study period or has any rapidly progressing disease or immediate life-threatening illness (e.g. cancer). In addition, any subject who has any other condition (e.g. neurological condition) that is likely to affect respiratory function should not be included in the study.
9. **Hospitalization:** Hospitalization for COPD or pneumonia within 12 weeks prior to Visit 1. **Pneumonia and/or moderate COPD exacerbation** that has not resolved at least 14 days prior to Screening Visit 1 and at least 30 days following the last dose of oral/systemic corticosteroids (if applicable).
10. **Inhaled corticosteroids (ICS):** Had received ICS or ICS/LABA for the treatment of COPD in the 6 weeks prior to Screening Visit 1
11. **Exacerbation:** Had >1 moderate exacerbation in the 12 months prior to Screening Visit 1, or one severe exacerbation requiring hospitalisation in the 12 months prior Screening Visit 1.
12. **Other respiratory tract infections** that have not resolved at least 7 days prior to Screening V1.
13. **Lung Resection:** Subjects with lung volume reduction surgery (including procedures such as endobronchial valves) within the 12 months prior to Screening V1.
14. **Oxygen:** Use of long-term oxygen therapy (LTOT) described as resting oxygen

therapy >3L/min at screening required to maintain adequate oxygenation (e.g. $S_aO_2 >90\%$). (Oxygen use $\leq 3L/min$ flow is not exclusionary, and patients may adjust oxygen levels up or down as needed during the study.)																																	
CONCOMITANT MEDICATIONS																																	
15.	Medications prior to Screening: Use of the following medications according to the following defined time intervals prior to Screening (Visit 1) or during the study:																																
	
  
 Medication	No use within the following time intervals prior to Screening and thereafter at any time during the study	
   
 Inhaled corticosteroids (ICS)	6 weeks	
 
 Depot corticosteroids	12 weeks	
 
 Systemic, oral or parenteral corticosteroids^a	6 weeks	
 
 Antibiotics (for lower respiratory tract infection)	6 weeks	
 
 Phosphodiesterase 4 (PDE₄) Inhibitor (e.g roflumilast)	14 days	
 
 LABA/Inhaled Corticosteroid (ICS) combination products	6 weeks	
 
 LABA/LAMA combination products	2 weeks	
 
 Theophyllines	48 hours	
 
 Oral beta₂-agonists		
 
  Long-acting	48 hours	
 
  Short-acting	12 hours	
 
 Inhaled short acting beta₂-agonists^b	4 hours	
 
 Inhaled short-acting anticholinergics	4 hours	
 
 Inhaled short-acting anticholinergic/short-acting beta₂-agonist combination products	4 hours	
 
 Any other investigational medication	30 days or within 5 drug half-lives (whichever is longer)	
  
	Medication	No use within the following time intervals prior to Screening and thereafter at any time during the study	Inhaled corticosteroids (ICS)	6 weeks	Depot corticosteroids	12 weeks	Systemic, oral or parenteral corticosteroids ^a	6 weeks	Antibiotics (for lower respiratory tract infection)	6 weeks	Phosphodiesterase 4 (PDE ₄) Inhibitor (e.g roflumilast)	14 days	LABA/Inhaled Corticosteroid (ICS) combination products	6 weeks	LABA/LAMA combination products	2 weeks	Theophyllines	48 hours	Oral beta ₂ -agonists		Long-acting	48 hours	Short-acting	12 hours	Inhaled short acting beta ₂ -agonists ^b	4 hours	Inhaled short-acting anticholinergics	4 hours	Inhaled short-acting anticholinergic/short-acting beta ₂ -agonist combination products	4 hours	Any other investigational medication	30 days or within 5 drug half-lives (whichever is longer)
Medication	No use within the following time intervals prior to Screening and thereafter at any time during the study																																
Inhaled corticosteroids (ICS)	6 weeks																																
Depot corticosteroids	12 weeks																																
Systemic, oral or parenteral corticosteroids ^a	6 weeks																																
Antibiotics (for lower respiratory tract infection)	6 weeks																																
Phosphodiesterase 4 (PDE ₄) Inhibitor (e.g roflumilast)	14 days																																
LABA/Inhaled Corticosteroid (ICS) combination products	6 weeks																																
LABA/LAMA combination products	2 weeks																																
Theophyllines	48 hours																																
Oral beta ₂ -agonists																																	
Long-acting	48 hours																																
Short-acting	12 hours																																
Inhaled short acting beta ₂ -agonists ^b	4 hours																																
Inhaled short-acting anticholinergics	4 hours																																
Inhaled short-acting anticholinergic/short-acting beta ₂ -agonist combination products	4 hours																																
Any other investigational medication	30 days or within 5 drug half-lives (whichever is longer)																																
a-	Corticosteroids are allowed for the treatment of COPD exacerbations during the double-blind treatment phase of the study. Localized corticosteroid injections (e.g., intra-articular and epidural) are permitted.																																
b-	Use of study provided albuterol/salbutamol is permitted during the study, except in the 4-hour period prior to spirometry testing																																
16.	Medication prior to spirometry: Unable to withhold albuterol/salbutamol for the 4 hour period required prior to spirometry testing at each study visit. Unable to withhold morning dose of subject's inhaled LABA or LAMA COPD medication prior to spirometry testing at Screening Visit (Visit 1).																																
17.	Maintenance use of short-acting bronchodilators: Regular use (prescribed for daily/ regular use, not for as-needed use) of short-acting bronchodilators (e.g. albuterol/salbutamol).																																

RELEVANT HABITS	
18.	Drug or alcohol abuse: A known or suspected history of alcohol or drug abuse within 2 years prior to Screening Visit 1 that in the opinion of the investigator

would prevent the subject from completing the study procedures.
CONTRAINDICATIONS
19. Any history of allergy or hypersensitivity to any anticholinergic/muscarinic receptor antagonist, sympathomimetic, lactose/milk protein or magnesium stearate.

DIAGNOSTIC ASSESSMENTS AND OTHER CRITERIA
20. Pulmonary Rehabilitation program: Participation in the acute phase of a pulmonary rehabilitation program within 4 weeks prior to Screening Visit 1. Subjects who are in the maintenance phase of a pulmonary rehabilitation program are not excluded.
21. Affiliation with investigator sites: Is an investigator, sub-investigator, study coordinator, employee of a participating investigator or study site, or immediate family member of the aforementioned that is involved in this study
22. Inability to read: In the opinion of the investigator, any subject who is unable to read and/or would not be able to complete questionnaires on the electronic diary.

Subjects who fail to meet inclusion and exclusion criteria at the **Screening Visit 1** will be considered screen failures and cannot be **re-screened**.

5.3. Randomization Criteria

In order to be randomized to one of the 3 treatment arms at Visit 2, subjects must have completed the run-in period and must have fulfilled all inclusion and exclusion criteria described in Section 5.1 and Section 5.2. In addition to the following:

REQUIRED CRITERIA FOR RANDOMIZATION AND TREATMENT
1. COPD Exacerbation: Subjects must not have experienced a moderate or severe COPD exacerbation or a lower respiratory tract infection during run-in or at Day 1 (Visit 2) inclusive. A moderate exacerbation is defined as worsening of symptoms of COPD requiring the use of antibiotics or systemic corticosteroids. A severe exacerbation is defined as worsening symptoms of COPD requiring hospitalization.
2. CAT score: A CAT score of ≥ 10 at Visit 2
3. Prohibited Medications: No use of any prohibited medications during the run-in period or at Visit 2, including any ICS or ICS/LABA combination. Subject's inhaled LABA or LAMA medication morning dose must be withheld and discontinued at Visit 2.
4. Any change to COPD medications: Including dosage and regimen during the run-in
5. Completion of electronic diary: Must have completed the electronic diary for at least 80% of days during the run-in period

Subjects who do not meet the required criteria for randomization at Visit 2 will not be randomized.

5.4. Screening/Baseline/Run-in Failures

Pre-screen, screen and run-in failures are defined as follows:

- Pre-screening failures: A subject, who is assigned a subject number at the Pre-screening Visit 0 but does not have any Screening Visit 1 procedures, will be considered a pre-screen failure.
- Screening failures: Those subjects that complete at least one Screening Visit 1 procedure but do not enter the run-in period.
- Run-in failures: Those subjects that enter the run-in period but are not randomized to any of the study treatment arms.

Subjects who are pre-screen, screen and run-in failure will be recorded in the eCRF. In order to ensure transparent reporting of screen failure subjects, meet the Consolidated Standards of Reporting Trials (CONSORT) publishing requirements, and respond to queries from Regulatory Authorities, a minimal set of screen failure information is required to be recorded in eCRF including demography, screen failure details, eligibility criteria, and serious adverse events (Section [7.4.1](#)).

5.5. Withdrawal/Stopping Criteria

5.5.1. Withdrawal from the Study

Subjects may be withdrawn from the study at any time by the Investigator if it is considered to be detrimental for them to continue in the study. Reasons for withdrawal from study treatment can include: an AE, clinically significant abnormality, lack of efficacy, sponsor terminated study, pregnancy, or for any other reason.

If a subject withdraws from the study, he/she may request destruction of any samples taken, and the investigator must document this in the site study records.

A reason for the withdrawal from the study must be captured in the electronic case report form (eCRF).

Stopping Criteria

A subject must be withdrawn from the study, in consultation with the medical monitor and principal investigator, if any of the following stopping criteria are met:

- **Liver Chemistry:** Meets any of the Liver chemistry stopping criteria (See Section [5.5.3](#))
Note: clinical laboratory assessments are not required for this study. However, laboratory samples may be taken for liver event analysis, if clinically indicated by the study investigator.
- **Pregnancy:** Positive pregnancy test (see [Appendix 7](#))

- **Unstable or life threatening cardiac events:** myocardial infarction, hospitalization for unstable angina, stroke, and other cardiovascular events considered life- or intensively health-threatening by the study physician.
- **COPD Exacerbations:** Subjects with two moderate or one severe COPD exacerbation during the study.
- **Withdrawal from study treatment** requires withdrawal from the study.
- **Non-Compliance with Study treatment:** Subjects' compliance with study treatment will be assessed at each study visit. Subjects who are non-compliant should be re-educated on the requirement for treatment compliance. Every effort will be made to keep subjects in the study and to re-educate those subjects who continue to be non-compliant. Subjects who continue to be non-compliant after multiple visit assessments may be permanently discontinued **after consultation with the GSK clinical team.**
- **Non-Compliance with eDiary:** Subjects must be compliant in completing their eDiary between each pair of on-treatment visits. Subjects who are non-compliant should be re-educated on the requirement for daily diary entry compliance. Subjects who continue to be non-compliant after multiple visit assessments may be permanently discontinued **after consultation with the GSK clinical team.**

Subjects withdrawn from study treatment will not be replaced.

The following actions must be taken in relation to a subject who fails to attend the clinic for a required study visit:

- The site must attempt to contact the subject and re-schedule the missed visit as soon as possible.
- The site must counsel the subject on the importance of maintaining the assigned visit schedule and ascertain whether or not the subject wishes to and/or should continue in the study.
- In cases where the subject is deemed 'lost to follow up', the investigator or designee must make every effort to regain contact with the subject (where possible, 3 telephone calls and if necessary a certified letter to the subject's last known mailing address or local equivalent methods). These contact attempts should be documented in the subject's medical record.
- Should the subject continue to be unreachable, only then will he/she be considered to have withdrawn from the study with a primary reason of "Lost to Follow-up".

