7.3.4. COPD Exacerbation

A mild exacerbation is defined as worsening of symptoms that require no treatment with antibiotics or steroids, and is self managed by the patient by an increase of inhaled rescue medications. A moderate COPD exacerbation is defined as worsening symptoms of COPD that require treatment with oral/systemic corticosteroids and/or antibiotics. A severe exacerbation is defined as worsening symptoms of COPD that require in-patient hospitalization or emergency room for longer than 24 hrs.

If a subject experiences a mild, moderate or severe COPD exacerbation, the COPD exacerbation page of the eCRF should be completed. COPD exacerbations should not be recorded as an AE, unless they meet the definition of a SAE. Details of COPD exacerbation identification, categorization and treatment guidelines are described in [Appendix 5](#).

Subjects who experience a mild exacerbation during the run-in period will not be withdrawn from the study. However, subjects who experience moderate or severe exacerbation during the run-in period will be withdrawn from the study and will not be allowed to be re-screened.

Subjects, who experience a mild, moderate or severe exacerbation during the treatment period, will **not** be withdrawn from the study unless the investigator or GSK medical monitor thinks it is best for the patient to withdraw from the study.

Signs and symptoms of COPD included on the electronic diary cards will not be considered AEs and will not be recorded in the eCRF.

The time period for collection of COPD exacerbations will be from the Pre-Screening (Visit 0) until completion of the follow-up contact. If a subject experiences a COPD exacerbation from the time the ICF is signed until randomization, summary information (yes/no status question) will be collected in the eCRF. COPD exacerbations after randomization through follow-up will be recorded on the COPD exacerbation page of the eCRF.

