Appendix 4, Section 12.4.4, second bullet point

Revised text:

The investigator will then record all relevant information regarding an AE/SAE in the electronic CRF "and/or paper form as applicable". Added

Section 12.4.6, second bullet point

Revised text:

"For lack of efficacy reports the paper form will be used to submit to GSK as per the table in Section 12.4.1 above". Added

12.9.3. Protocol Amendment 3

Protocol changes for Amendment 03, from protocol changes to amendment 02 (21-Feb-2014)

Scope: This amendment applies to all sites

Amendment 03 Summary and Rationale

Strike through text refers to deleted text and underlined refers to added text.

List of Specific Changes

Section 1 Objective(s)/Endpoint(s) and Section 3 Objective(s)/Endpoint(s)

Rationale for change: Rate of COPD exacerbations endpoints from tertiary to exploratory due to stopping criteria.

Revised text:

Exploratory	

 • To explore the effect of UMEC/VI (62.5/25 mcg once daily), UMEC (62.5 mcg once daily) with salmeterol (50 mcg twice daily) on rate of COPD exacerbation 	
 • Rate of mild, moderate or severe exacerbations • Rate of moderate or severe exacerbation

Section 1. Overall Design

Rationale for change: To clarify study design and content of section to agree with Section 4.1

Revised text:

There will be a total of 5 clinic visits and one follow-up phone call (Visit 6). A pre-screening visit (Visit 0) may be required in order to administer the informed consent before any changes are made to the subject's current medication regimen. If no changes in medication are required, V0 (pre-screening) and V1 (screening) may be conducted on the same day. Inhaled long-acting muscarinic antagonist (LAMA) or long-acting beta₂-agonist (LABA) and/or albuterol/salbutamol as needed (rescue medication) are not exclusionary prior to Screening or during the run-in.

Eligible subjects at Screening Visit 1 will be current or former smokers, at least 6 weeks ICS and ICS/LABA free with an FEV₁ post-albuterol/salbutamol of $\geq 30\%$ to $\leq 80\%$ predicted normal and a FEV₁/FVC < 0.7 and a CAT score ≥ 10 .

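### Sections 5.5.1 and 7.3.4 conflict on whether a subject with a severe or second moderate on-treatment exacerbation is withdrawn, so the rule a site follows decides whose Week 24 data are missing

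*Protocol*

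**What the plan says.** The list of stopping criteria in Protocol Section 5.5.1 is headed by a mandatory instruction: "A subject must be withdrawn from the study, in consultation with the medical monitor and principal investigator", whenever a listed criterion applies. One of the criteria is "Subjects with two moderate or one severe COPD exacerbation during the study". The same list states that stopping study treatment "requires withdrawal from the study".

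Section 7.3.4 covers an on-treatment event of any severity and sets a different default: "mild, moderate or severe exacerbation during the treatment period, will not be withdrawn from the study unless the investigator". The one exception it names is a judgement, by that person or by the sponsor's medical monitor, that leaving is in the subject's interest.

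Both sections belong to the current (Amendment 3) text. The change log in Section 12.9.3 gives this reason for moving one group of endpoints: "Rate of COPD exacerbations endpoints from tertiary to exploratory due to stopping criteria".

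Section 9.4.1 analyses Week 24 trough FEV1 and TDI by MMRM, using Weeks 4, 12 and 24, without imputation and under a missing-at-random assumption. Section 9.2 allows for 10% withdrawal.

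**The concern.** For some subjects one section orders withdrawal and the other makes staying the default. No precedence rule says which section governs. Section 7 of the protocol permits no waivers except for immediate safety concerns, so a site that follows one section departs from the other. Staff managing an exacerbation are likely to look first at Section 7.3.4 and Appendix 5. Section 12.5.3 of that appendix discusses stopping the investigational product temporarily and does not mention the stopping criterion.

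Two things are at stake. Identical subjects may be removed at one site and kept at another. And because the choice depends on exacerbation, the set of subjects without Week 24 values depends on disease course and on which section a site read.

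**Working it through.** **Step 1. The two rules by type of on-treatment event.**

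| Event | Section 5.5.1 | Section 7.3.4 | Compatible? |
|---|---|---|---|
| Mild | no trigger | stays unless judged otherwise | yes |
| First moderate | no trigger | stays unless judged otherwise | yes |
| Second moderate | must be withdrawn | stays unless judged otherwise | no |
| Severe | must be withdrawn | stays unless judged otherwise | no |

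**Step 2. Origin.** The Amendment 2 protocol is reproduced after the current text. Its Section 5.5.1 has no exacerbation stopping criterion, and its Section 7.3.4 already has the sentence against withdrawal. Section 12.9.3 records the criterion as an Amendment 3 change to Section 5.5.1 and lists no change to Section 7.3.4. The 10% allowance in Section 9.2 is the same in both versions.

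**Step 3. What a withdrawn subject loses.** In the Section 7.1 table, the Early Withdrawal column has no entry for spirometry, TDI, SGRQ-C, CAT or the global ratings. It does include adverse events and exacerbations, and the Visit 6 contact (Section 5.6) collects both again. The loss is therefore the later spirometry and patient-reported data, including all Week 24 values. The MMRM in Section 9.4.1 does not name exacerbations among its covariates, so missingness triggered by them is not addressed directly by the model.

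**Step 4. Which event endpoints depend on the rule.**
- Exacerbation rates (exploratory): affected, because follow-up stops at the trigger under one rule only.
- Time to severe exacerbation: a severe event is itself the trigger, so it is observed. Only subjects removed after a second moderate event lose later follow-up for a severe one.
- Time to first exacerbation, and to first moderate or severe exacerbation: the event falls at or before the trigger, so these are essentially unaffected.
- Time to CID: a moderate or severe on-treatment exacerbation is a CID component (Section 7.3.5), and the version without FEV1 keeps it. Anyone reaching the trigger has already had a CID, so this too is essentially unaffected.

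**Step 5. Sample size reproduced (Section 9.2).** Inputs: TDI SD 2.94, difference 0.5, two-sided 5%, 90% power. n = 2 × 2.94² × (1.960 + 1.282)² / 0.5² gives 727 per arm. 727 / 0.90 = 808 per arm, and 808 × 3 = 2424. Trough FEV1 with difference 80 mL and SD 240 mL at n = 727 gives power above 99.9%. All agree with the protocol.

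**Step 6. Power if total withdrawal were higher.** Power = Φ(difference / (SD × √(2/n)) − 1.96), with n = 808 × (1 − withdrawal). The withdrawal rates above 10% are assumptions.

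| Total withdrawal | n per arm | TDI power | FEV1 power |
|---|---|---|---|
| 10% (planned) | 727 | 90.0% | >99.9% |
| 12% | 711 | 89.4% | >99.9% |
| 15% | 687 | 88.3% | >99.9% |
| 20% | 646 | 86.4% | >99.9% |
| 25% | 606 | 84.1% | >99.9% |
| 30% | 566 | 81.6% | >99.9% |

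**Step 7. How many subjects the trigger could reach (illustration).** The protocol gives no exacerbation rate. Assume 0.3 to 0.6 moderate and 0.05 to 0.10 severe events per patient-year, independent Poisson counts, and 24/52 year of follow-up.
- P(two or more moderate) = 1 − e^(−λ)(1 + λ), with λ = rate × 24/52: 0.9% to 3.2%.
- P(one or more severe) = 1 − e^(−λ): 2.3% to 4.5%.
- Either: 3.1% to 7.6%, about 76 to 183 of 2424.

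**The case against.** The best defence is that the two sections nearly meet in practice. Section 5.5.1 requires consultation with the medical monitor and principal investigator, Section 7.3.4 lets the investigator or medical monitor withdraw a subject, and Section 5.5.2 lists COPD exacerbation as a withdrawal reason. Many subjects with a severe event might leave under either section. That stands as a limit on size: the 3.1% to 7.6% counts everyone meeting the trigger, so the difference between the rules is smaller. It does not remove the conflict. Consultation does not cancel a mandatory instruction, and discretion to withdraw does not turn a default of staying into one.

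A second defence is that the sponsor saw the effect on exacerbation rates and made them exploratory. That is fair, and it limits the importance of those endpoints. It does not cover Week 24 FEV1 or the patient-reported outcomes.

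A reader might infer more than the documents support:
- *That the rules are opposite for every subject who exacerbates.* They differ only in the last two rows of the first table.
- *That withdrawal ends all data collection.* Adverse events and exacerbations are still collected at the Early Withdrawal visit and the follow-up contact.
- *That the 10% allowance must be wrong under one rule.* Section 9.2 gives a total with no breakdown by cause, and 3.1% to 7.6% fits within it. What can be said is that the figure did not change when the criterion was added.
- *That the trial becomes underpowered.* Even if all of the 3.1% to 7.6% came on top of 10%, total withdrawal would be 13.1% to 17.6%. TDI power would then lie between the 12% and 20% rows, and primary power would not move materially.

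**Conclusion.** The contradiction is real, lies in current text and is confined to severe and second moderate on-treatment exacerbations. It needs correcting because sites cannot comply with both sections, and because the section followed determines which of these subjects have no Week 24 trough FEV1 or patient-reported values under a missing-at-random analysis. It also affects the exploratory exacerbation rates and severe-event follow-up after a second moderate event.

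The resulting bias cannot be sized from the protocol: it would depend on exacerbation rates by arm and on how sites divide between the two readings, and neither is given. The 3.1% to 7.6% is an assumption-based upper guide to the number of subjects involved. The case rests on inconsistent conduct and outcome-related missingness. Power, time to first exacerbation and time to CID are not part of it.

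**What to change.** Reconcile Sections 5.5.1 and 7.3.4 so that a single rule for severe and second moderate on-treatment exacerbations is stated identically in both and applied at all sites. Which rule stands is a clinical decision for the sponsor, and this review takes no position on it. Then recheck the 10% withdrawal assumption in Section 9.2 against the rule kept, and either confirm it or revise it.

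The cost is amendment wording in two sections and a letter to sites. No change to the primary analysis model or the randomisation is needed.
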